7. STUDY POPULATION

This study will be conducted in approximately 30 adult female and male subjects (18 to 50 years of age) with a documented medical diagnosis of classic 21-hydroxylase deficiency CAH. Subjects must meet all inclusion criteria and no exclusion criteria in order to be enrolled. Subjects who previously completed the current study in Cohort 1 or Cohort 2 may reenroll to participate in Cohorts 3 or 4 (in addition to new subjects). Subjects who reenroll and have had a stable medication regimen for CAH since their last visit in this study do not have to undergo screening; those who reenroll and have had a change to their medication regimen for CAH must undergo a second screening visit.

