7.2. Subject Exclusion Criteria

Subjects will be excluded from the study if they:

- 1. Have a clinically significant unstable medical condition or chronic disease (including history of neurological, hepatic, renal, cardiovascular, gastrointestinal, pulmonary, psychiatric or endocrine disease [excluding CAH]), or malignancy that could confound interpretation of study outcome.
- 2. Had a clinically significant illness within 30 days of screening.

- Have a known or suspected diagnosis of any of the other known classic forms of CAH including 11β-hydroxylase deficiency, 17β-hydroxylase deficiency, 3β-hydroxysteroid dehydrogenase deficiency, P450 side-chain cleavage deficiency, or P450 oxidoreductase deficiency.
- Have a history that includes bilateral adrenalectomy, hypopituitarism, or other condition requiring daily therapy with orally administered glucocorticoids (eg, asthma, arthritis, or systemic lupus erythematosus).
- 5. Have any clinically significant acute or unstable chronic abnormal finding in physical examination, neurological assessment, vital signs, ECGs, or clinical laboratory tests, as determined by the investigator.
- 6. Are pregnant or lactating females.
- 7. Have a history of epilepsy or serious head injury (eg, traumatic brain injury or postconcussive syndrome).
- 8. Have a known history of long QT syndrome or cardiac tachy-arrhythmia.
- Have a screening or baseline (Day 1) average ECG corrected QT interval using Fridericia's formula (QTcF) of >450 msec (males) or >470 msec (females) or the presence of any clinically significant cardiac abnormality.
- 10. Have an exaggerated pharmacological sensitivity (ie, hypersensitivity) to any corticotropin releasing hormone antagonists.
- 11. Test positive at screening for hepatitis B surface antigen (HBsAg), hepatitis C antibody (HCV-Ab), or human immunodeficiency virus antibody (HIV-Ab), or have a history of a positive result.
- 12. Have a recent history (≤1 year before screening) of alcohol or drug abuse, or current evidence of substance dependence or abuse criteria.

- 18. Used any other investigational drug within 30 days or 5 half-lives (whichever is longer) before initial screening, or plans to use an investigational drug (other than the study drug) during the study. Subjects who previously completed the current study in Cohort 1 or Cohort 2 may reenroll to participate in Cohorts 3 or 4; these subjects do not need to meet this criterion with respect to NBI-74788.

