- 19. Use of any excluded concomitant medication (refer to Section 8.10.1) within 30 days of screening.
- 20. Have a significant risk of suicidal or violent behavior. Subjects with any suicidal ideation of type 4 (active suicidal ideation with some intent to act, without specific plan) or type 5 (active suicidal ideation with specific plan and intent) in the past 6 months before screening or lifetime history of suicidal behavior based on the Columbia-Suicide Severity Rating Scale (C-SSRS) should be excluded.
- 21. Have ingested foods containing poppy seeds within 7 days before screening, the start of the 24-hour PD baseline period (Day -7), and Day 1.
- 22.
- 23. Have had a blood loss ≥550 mL or donated blood within 30 days before at the start of the 24-hour PD baseline period (Day -7).
- 24. In the Investigator's opinion, the subject is not capable of adhering to the protocol requirements.
- 25. Have a known allergy, hypersensitivity, or intolerance to any component of vanilla-flavored (eg, soy) (Cohorts 1 and 2 only).

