Weight	X		Х					Х				Х
Vital Signs	X	X	Х		Х		Х	Xf				Х
12-lead ECG ^g	X		Х				Х	Х				Х
Pregnancy test ^h	X (s)	X (s/u)	X (u)				X (u)					X (u)
Screening FSH (postmenopausal females only)	X											
Serology (HBsAg, HCV-Ab, HIV-Ab)	Х											
Morning 17-OHP ^j	Х											
Clinical laboratory tests ^k	X		Х		Х			Х				Х
Urine drug screen & alcohol breath test ¹	Х	Х	X				Х					
PD blood samples ^m	X	Х			Х		Х	Х	Х	Х	Х	Х
Brief Psychiatric Rating Scale ⁿ			Х				Х	Х				Х
C-SSRS	Х	X°	Х					Х				Х
PK plasma samples ^p					Х		Х	Х	Х	Х	Х	Х
Study drug dosing ^q			Х	Х	Х	Х	Х					
Subject study diary ^r			Х	Х	Х	Х	Х					
Study drug reconciliation ^s					Х		Х					
AE monitoring	Х	Х	Х	Х	Х	Х	Х	Х	Х	Х	Х	Х
Prior and concomitant medications	X	X	Х	Х	Х	Х	Х	Х	X	X	X	Х
Center visit	X		X		Х				X ^t	Xt	X ^t	Х
Inpatient center stay		Х					Х	Х				

Table 3:Schedule of Assessments for Cohorts 3 and 4

Definitions and footnotes are on the next page.

- Definitions: 17-OHP=17-hydroxyprogesterone; AE=adverse event; C-SSRS=Columbia-Suicide Severity Rating Scale; ECG=electrocardiogram; FSH=follicle stimulating hormone; HBsAg=hepatitis B surface antigen; HCV-Ab=hepatitis C virus antibody; HIV-Ab=human immunodeficiency virus antibody; PD=pharmacodynamic; PK=pharmacokinetic; s=serum; u=urine.
- ^a Subjects who reenroll and have had a stable medication regimen for CAH since their last visit in this study do not have to undergo screening; those who reenroll and have had a change to their medication regimen for CAH must undergo a second screening visit.
- ^b Final study visit for subjects who complete the study (or early termination). The final study visit will be conducted approximately 5 weeks (+7 days) after the last dose of study drug.
- ^c Day 1 occurs 1 week after the Day -7 visit. Day 1 assessments will be collected predose unless otherwise noted below. Safety assessments collected predose on Day 1 will serve as the baseline.
- ^d Only for subjects who reenroll and who do not undergo screening.
- ^e Only for subjects who undergo screening.
- ^f Vital signs will be collected on Day 15 between 8-10 and 22-24 hours postdose (ie, morning and evening) (for Cohort 4, timing is relative to evening dosing).

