8.5.2. Medical History and Physical Examination

A medical history will be taken at the screening visit and updated on Day -7 and Day 1 (only for subjects who undergo screening).

A complete physical examination including weight will be conducted at screening, on Day 1, Day 2 (Cohorts 1 and 2 only), Day 7, Day 15, and Day 49 (or final study visit for subjects who terminate early). The complete physical examination will consist of an assessment of general appearance, skin and mucosae, head, eyes, ears, nose, throat, neck (including thyroid), lymph nodes, chest/lungs, cardiovascular, abdomen, extremities, neurological and musculoskeletal systems. Height and weight will be measured with subjects not wearing shoes. Height will be measured only at screening. Weight will be measured at screening, on Day 1, Day 15, and Day 49 (or final study visit for subjects who terminate early).

8.5.3. 12-Lead Electrocardiogram

12-lead ECG will be conducted in triplicate (1-3 minutes apart) after the subject has rested supine for at least 5 minutes at the following times (for Cohort 4, all times are relative to evening dosing):

- Screening.
- Days 1 and 14 (predose).
- Days 2 and 15: prior to visit completion or discharge (Day 2 only applies to Cohorts 1 and 2).
- Day 49 (or final study visit for subjects who terminate early).

The ECG parameters that will be assessed include heart rate, PR interval, QRS duration, QT interval, and QTcF (machine readings). Additionally, the occurrence of de- and re-polarization and rhythm disorders or other abnormalities will be assessed. Based on the review of these
parameters, the investigator or designee will note if the ECG is Normal, Abnormal Not Clinically Significant, or Abnormal Clinically Significant. If the ECG is Abnormal Clinically Significant, the investigator will provide a description of the abnormality recorded on the AE eCRF.

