8.8.2. Day -7 to Day -6: 24-Hour Baseline Pharmacodynamics

Subjects who reenroll and do not undergo screening must provide subject informed consent.

Subjects who continue to meet eligibility requirements will return to the study center for a 24-hour in-patient stay, during which blood samples will be collected for PD analysis. Subjects will not take their usual morning dose of steroidal treatment until after the 1000 hours PD sample is collected on Day -6.

The following study evaluations and tasks will be performed on Day -7 to Day -6:

- Update inclusion/exclusion criteria and medical history (only for subjects who undergo screening).
- Collect vital signs.
- Perform a urine (for subjects who undergo screening) or serum (for subjects who did not undergo screening) pregnancy test (β-hCG) for female subjects of childbearing potential.
- Collect urine for drug screen and perform alcohol breath test. Urine testing kits will be provided by the central laboratory to confirm negative drug screen prior to PD collection. A separate urine sample will also be sent to the central laboratory for analysis.
- Collect blood samples for PD biomarkers (17-OHP, androstenedione, testosterone, cortisol, and ACTH) at: approximately 1845, 2000, 2100, 2200, 2300, 2400, 0100, 0200, 0400, 0600, 0800, 1000, 1200, 1400, 1800, 1900, and 2200 hours.
- Administer the C-SSRS (Screening/Baseline version) only for subjects who reenroll and who do not undergo screening.
- AE monitoring.
- Record prior medications.

Eligible subjects will be instructed to return to the study center on Day 1.

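### Cohort 3/4 subjects who re-enrol without screening have no scheduled general eligibility review or medical-history update before their second course, although Section 7 still requires them to be eligible

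*Combined protocol and SAP*

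**What the plan says.** Sections 6.1, 7 and 8.8.1 let subjects who completed Cohort 1 or 2 re-enrol in Cohort 3 or 4. Those with a stable CAH medication regimen since their last study visit skip screening; those with a changed regimen are screened again.

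For Cohorts 3 and 4, the criteria are assessed and the history taken at screening (8.8.1). Both are updated at Day -7 and Day 1, but only for some subjects:

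- Section 8.8.2 (Day -7): "Update inclusion/exclusion criteria and medical history (only for subjects who undergo screening". Section 8.8.3.1 repeats this for Day 1.
- Section 8.5.2: the history is "updated on Day -7 and Day 1 (only for subjects who undergo screening".
- Table 3 footnote e, attached to both updates at both visits: "Only for subjects who undergo screening".

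The duty to be eligible is kept. Section 7 says "Subjects must meet all inclusion criteria and no exclusion criteria in order to be enrolled", in the paragraph that permits re-enrolment. Section 8.8.2 opens with "Subjects who continue to meet eligibility requirements will return to the study center". Exclusion 18 carries an express exemption for re-enrollers: "these subjects do not need to meet this criterion with respect to NBI-74788". It is the only one visible; exclusions 13 to 17 and 22 cannot be read in the public text.

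**The concern.** The plan requires eligibility of every enrolled subject, then removes, for one group, the only general task that would establish and record it. A site that follows the visit lists could start a second course without asking about illness or blood loss since the first, and without documenting that the criteria are met.

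The waiver is triggered by CAH medication alone, so a new non-CAH condition does not by itself bring back either screening or a history update. AEs are recorded from consent to the final study visit (Section 10). A new event that starts and resolves between the first final visit and the second consent is therefore seen only if it leaves a mark on the medication record or a later test. Exclusion 1 concerns conditions that could confound the study outcome, so both safety and the interpretation of the biomarker data are involved.

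**Working it through.** No sample-size, power or error-rate figure is involved. The check is a comparison of sections plus a day count.

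**1. Scheduled general reviews, Cohort 3/4 course**

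| Visit | Screened subject | Unscreened re-enroller |
|---|---|---|
| Screening (8.8.1) | criteria and history | visit skipped |
| Day -7 (8.8.2, 8.5.2, footnote e) | both updated | excluded |
| Day 1 (8.8.3.1, 8.5.2, footnote e) | both updated | excluded |
| Day 7 to final visit (8.8.3.2 to 8.8.4.2) | none listed | none listed |
| Total | 3 | 0 |

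**2. Is this a planned route?** With no Day 0, Day -7 to Day 49 covers 7 + 49 = 56 days = 8 weeks. Adding 3 weeks of screening gives 11. Section 8.9 gives an additional 8 to 11 weeks for re-enrollers, so the unscreened course is foreseen.

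**3. Age of the last general review.** For Cohorts 1 and 2 the last scheduled update is first-course Day 1 (8.7.3.1). Re-enrolment requires completion, taken here as attending the final visit.

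- Day 1 to Day 49: 49 - 1 = 48 days. This is the minimum age at the second Day -7, if that falls on the first final visit.
- Day -7 to Day 1 is 7 days, so the minimum age at the second Day 1 is 48 + 7 = 55 days.
- If the final visit uses its full +7 days: 48 + 7 = 55 and 55 + 7 = 62 days.
- No maximum interval between courses is stated, so there is no upper bound.

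**4. What still happens for this group.** At Day -7: new consent, Screening/Baseline C-SSRS, serum pregnancy test, drug and alcohol tests, vital signs, AE monitoring and prior-medication recording. On Day 1: urine pregnancy test, drug and alcohol tests, vital signs, physical examination, ECG (QTcF feeds exclusion 9), laboratory tests, C-SSRS, and AE and medication recording. The first-course final visit also included examination, ECG, laboratory tests and C-SSRS (8.7.4.2).

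**5. What no listed step captures**

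- Illness or an unstable condition arising between courses that leaves no medication or test trace (exclusions 1 and 2).
- Exclusion 23: blood loss, or having "donated blood within 30 days before at the start of the 24-hour PD baseline period". Section 8.10.2 bans donation around each course, but no listed step confirms this or asks about loss.
- A documented eligibility decision.

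**6. Criteria tied to a visit that does not occur.** Exclusion 2 reads "Had a clinically significant illness within 30 days of screening". Exclusions 12, 19 and 20 and the 30-day prior-medication record (8.10.1) also look back from screening. For an unscreened second course that date is undefined. Inclusion 8 names a serum pregnancy test at screening and a urine test at Day -7, whereas 8.8.2 gives this group a serum test at Day -7. The instruction is clear, but the criterion does not match it.

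**The case against.** The strongest reply is that eligibility is not left unchecked. The C-SSRS at PD baseline is described as an eligibility evaluation (8.5.6), the Day 1 urine pregnancy test is marked as for eligibility (8.5.4), and inclusion 10 uses the Day -7 and Day 1 drug and alcohol tests. Exclusion 5 also lets the investigator act on examination, vital-sign, ECG and laboratory findings. This stands. A reader might infer that re-enrollers are dosed with no eligibility checks, and the documents do not support that.

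A reader might also take the 48 or 55 days as time without monitoring. That is wrong: AEs are recorded to the first final visit, and those ongoing then are followed further (10.5). In the minimum case, the interval between the first final visit and the second consent is 0 days.

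The waiver itself requires the site to establish that the CAH regimen has been stable, and 8.10.1 provides for corticosteroid augmentation during intercurrent stress. A significant illness may therefore surface through that enquiry or the medication record. Whether augmentation counts as a regimen change is not stated, and illness with no medication trace remains uncaptured.

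Finally, dosing a subject known to be ineligible would already breach Section 7. But Section 13.3 tells sites to follow instructions exactly, and the instruction here limits the update to screened subjects.

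**Conclusion.** The point holds as a conflict between stated rules: eligibility is required of everyone, while the general criteria and history updates are withheld from unscreened re-enrollers in four places. Its size is 0 scheduled general reviews against 3, with the last one at least 48 days old at the second Day -7 and 55 at the second Day 1. The lower bounds assume that the second Day -7 can fall on the first final visit; the interval has no stated upper limit. The number of subjects affected is not given and may be zero.

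The consequence is confined to interval history and documentation, because most objective safety checks are repeated. It would go too far to infer that the criteria were waived for this group, since Sections 7 and 8.8.2 say otherwise. Nor can it be said that exclusion 18 holds the only exemption, because some exclusions are not visible. The correction is worth making on safety grounds.

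**What to change.** Delete the parenthetical that limits the updates to screened subjects in Sections 8.8.2, 8.8.3.1 and 8.5.2, and delete Table 3 footnote e. Criteria and history are then updated at Day -7 and Day 1 for every Cohort 3/4 subject.

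Add one sentence to Section 7 reconciling the screening-anchored items with the waiver: inclusion 8, exclusions 2, 12, 19 and 20, and the prior-medication record. It should state the anchor date for unscreened re-enrollers and name the first-course screening results that carry over, such as serology and the qualifying 17-OHP sample that 8.2.1 already says is not repeated.

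The cost is protocol wording and a few minutes at two visits that already take place, with no new visit or blood sample. An occasional re-enrolling subject may be found ineligible.

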8.8.3. Treatment Period

The study will consist of a 14-day treatment period and will include an overnight in-patient stay (on Day 14 to Day 15) and study center visits on Days 1 and 7.

8.8.3.1. Day 1

Subjects will report to the study center on Day 1. The following study evaluations and tasks will be performed on Day 1:

- Update inclusion/exclusion criteria and medical history (only for subjects who undergo screening).
- Perform a physical examination including weight.
- Collect vital signs.
- Perform 12-lead ECG in triplicate (1-3 minutes apart).
- Perform a urine pregnancy test (β-hCG) for female subjects of childbearing potential.

- Collect blood sample for hematology and clinical chemistry.
- Collect urine sample for urinalysis.
- Collect urine for drug screen and perform alcohol breath test. Urine testing kits will be provided by the central laboratory to confirm negative drug screen prior to dosing. A separate urine sample will also be sent to the central laboratory for analysis.
- Administer the BPRS.
- Administer the C-SSRS (Since Last Visit version).
- AE monitoring.
- Record prior and concomitant medications.
- Instruct male subjects and female subjects of childbearing potential who do not practice total abstinence to continue using contraception.
- Instruct subjects to notify the investigator or study staff by telephone if they experience any AEs and before taking any concomitant medications.
- Instruct subjects to take study drug nightly at approximately 1900 hours through Day 13 (Cohorts 3 and 4) and at approximately 0700 hours through Day 14 (Cohort 4 only) as described in Section 9.3, and to document in the diary the date and time of study drug administration, the number of capsules taken, and confirmation that study drug was taken with breakfast (Cohort 4 only) and the evening meal each day.
- Instruct subjects to bring the subject study diary as well as the remaining study drug back for the Day 7 visit.
- Instruct subjects to delay their usual morning dose of concurrent steroidal treatments until approximately 1000 hours on Days 2 to 14.

Sites should call subjects between the Day 3 and Day 7 visits to remind them to complete the subject study diary, check on compliance, and remind them to bring subject study diary and remaining study drug to the Day 7 visit.

8.8.3.2. Day 7

The following procedures will be performed at the study center on Day 7:

- Perform a physical examination.
- Collect vital signs.
- Collect blood sample for hematology and clinical chemistry.
- Collect urine sample for urinalysis.
- Collect blood samples for PD biomarkers at 24 hours (-8 hour window) after the Day 6 dose and prior to the Day 7 dose for Cohort 3; 12 hours post morning dose but prior to the evening dose for Cohort 4 (-4 hour window).
- Collect blood samples for PK at 24 hours (-8 hour window) after the Day 6 dose and prior to the Day 7 dose for Cohort 3; 12 hours post morning dose but prior to the evening dose for Cohort 4 (-4 hour window).
- Check subject study diary.
- Study drug reconciliation.
- AE monitoring.
- Record concomitant medications.

The following additional procedures will be conducted on Day 7:

- Instruct subjects to perform study drug dosing (as described in Section 9.3) and subject study diary entry at home.
- Instruct subjects to return to the study center on Day 14 before dosing and to bring with them their study drug bottle including any unused study drug, and their subject study diary.

8.8.3.3. Day 14 to Day 15

Subjects will return to the study center on Day 14 and will be discharged in the evening of Day 15 after the 24-hour postdose procedures have been performed. Standard meals and snacks will be provided. The procedures to be conducted on these days are described in the following sections.

Day 14

Subjects will return to the study center on Day 14 (subjects in Cohort 4 will take their morning study drug dose at home). The following study evaluations and tasks will be performed prior to evening dosing on Day 14:

• Collect vital signs.

- Perform 12-lead ECG in triplicate (1-3 minutes apart).
- Perform a urine pregnancy test (β -hCG) for female subjects of childbearing potential.
- Collect urine for drug screen and perform alcohol breath test.
- Collect blood sample for PD biomarkers at 15 minutes predose.
- Collect blood sample for PK at 15 minutes predose.
- Administer the BPRS.
- Collect the study drug bottle including any unused study drug.
- Study drug reconciliation.
- AE monitoring.
- Record concomitant medications.

At approximately 1900 hours, each subject will receive study drug as described in Section 9.3 with a moderate fat/moderate calorie meal. Subjects should complete their evening meal within 30 minutes of taking study drug. After study drug dosing, subjects will record in the subject study diary the date and time of study drug administration, the number of capsules taken, and confirmation that study drug was taken with the evening meal. The subject study diary will then be collected.

The following procedures will be conducted after dosing on Day 14:

- Collect blood samples for PD biomarkers at 1, 2, 3, 4, and 5 hours postdose (±5 minute window).
- Collect blood samples for PK at 1, 2, 3, 4, and 5 hours postdose (±5 minute window).
- AE monitoring.
- Record concomitant medications.

Day 15

Subjects will delay their usual morning dose of steroidal treatment until after the 19-hour postdose PK/PD samples are collected (ie, at approximately 1400 hours).

The following procedures will be performed on Day 15:

- Perform a physical examination including weight.
- Collect vital signs between 8-10 and 22-24 hours post-evening dose (ie, morning and evening).
- Perform 12-lead ECG in triplicate (1-3 minutes apart).
- Collect blood sample for hematology and clinical chemistry.
- Collect urine sample for urinalysis.

- Collect blood samples for PD biomarkers at 6, 7, 9, 11, 13, 15, 17, 19, 23, 24, and 27 hours postdose (±15 minute window) (for Cohort 4, all times are relative to evening dosing).
- Collect blood samples for PK at 6, 7, 9, 11, 13, 15, 17, 19, 23, 24, and 27 hours postdose (±15 minute window) (for Cohort 4, all times are relative to evening dosing).
- Administer the BPRS.
- Administer the C-SSRS (Since Last Visit version).
- AE monitoring.
- Record concomitant medications.

The following procedures will be conducted before subjects may be discharged from the study center:

- Instruct male subjects and female subjects of childbearing potential who do not practice total abstinence to continue using contraception.
- Instruct subjects to notify the investigator or study staff by telephone if they experience any AEs and before taking any concomitant medications.
- Confirm if the subject prefers to have the Days 21, 28, and 35 visits conducted at home instead of at the study center.
 - If the subject elects to have a home visit, instruct him/her that the qualified home healthcare provider will contact him/her to schedule the visit.
 - If the subject elects to come into the study center, instruct him/her to return on Days 21, 28, and 35.

